8. STUDY INTERVENTION DISCONTINUATION AND PARTICIPANT DISCONTINUATION/WITHDRAWAL

8.1 DISCONTINUATION OF STUDY INTERVENTION

Discontinuation from the week of stimulation does not mean discontinuation from the study, and remaining study procedures should be completed as indicated by the study protocol. If a clinically

significant finding is identified (including, but not limited to changes from baseline) after enrollment, the investigator or qualified designee will determine if any change in participant management is needed.

The study intervention (i.e., the 5 consecutive days of stimulation) will be discontinued for the following reasons:

- A participant develops significantly increased suicidal risk, as determined by an acute assessment by [name] or [name].
- A participant has an ASRM score greater than or equal to 6.
- The participant misses a single day of stimulation and is unable to make it up at the end of the stimulation week.
- Any clinical adverse event (AE), laboratory abnormality, intercurrent illness or other medical condition, or situation occurs such that continued participation in the study would not be in the best interest of the participant.
- The participant meets any exclusion criteria (either newly developed or not previously recognized).

If the participant withdraws from the intervention, the participant will be contacted and invited for the FU1 survey questionnaires and for the FU2 follow-up assessment including all respective questionnaires. These assessments are not intended as a clinical follow-up with the participants but serve research purposes only.

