9.2.2 DEVELOPMENT OF MANIA

The Altman Self-Rating Mania Scale (ASRM) was designed to assess the severity of manic symptoms at enrolment, with the ability to track changes over the duration of participation. When undergoing treatment for depression, a possible side effect (as inferred from clinical trials with antidepressant medications) is to alter levels of serotonin, potentially associated with mania [18], [19]. Although we do not expect such an event to occur since there are no reports of inducing mania by tACS and we are not using a medication that targets serotonin levels, we will be conducting this assessment as a precautionary measure. If a participant develops any sign of mania (ASRM > 6), [name] or [name] will conduct an acute assessment to determine if the participant is experiencing mania. If this occurs during the week of stimulation, participation in the study will be stopped and their primary mental health care provider or family physician will be contacted. In the case that they do not see anyone for their mental health concerns, [name] or [name] will assist in creating a medical care plan.

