10.4.4 SAFETY ANALYSES

As discussed in *Section 8.2, Safety and Other Assessments* safety will be assessed with the C-SSRS, an adverse effects questionnaire, and the Altman Self-Rating Mania Scale (ASRM).

The C-SSRS will be used to assess suicide risk. If a participant's responses have an elevated risk, the participant will be contacted, and an acute assessment will be completed if deemed necessary by Dr.

[name] or [name] (as described above). Any verified increases in suicidal ideation will be described in counts/percentages. The C-SSRS is administered at the screening visit and at the 14-day follow up.

The stimulation questionnaire will be administered at D1-D5 after stimulation. This questionnaire solicits ratings of 11 possible sensory experiences ("flickering light") and adverse effects ("scalp pain") associated with electrical stimulation, on a scale of 0 (absent), 1 (low), 2(medium), and 3 (high). Intensity of sensory experiences and adverse effects will be described with mean and standard deviation.

The Altman Self-Rating Mania Scale (ASRM) will be used to assess any development of mania over the course of treatment. A ASRM score of greater than 6 indicates the possible development of a manic episode. Any participant who scores greater than 6 on the ASRM will be assessed by [name] or [name]. Any verified manic episode will be described in counts/percentages.

The Adverse Events Structured Interview will be administered by research personnel at D5 and whenever a participant spontaneously reports a potential AE during trial participation. This interview solicits open-ended descriptions of 13 possible adverse effects a participant may experience in any clinical trial as well as one question of 'any other experiences'. Responses will be reviewed by the clinician and rated as described in **Section 8.3.** Severity per adverse effect will be described with mean and standard deviation.

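### Stimulation stops at ASRM 6 or above (8.1), but a mania assessment is mandated only above 6 (9.2.2, 10.4.4), so a score of exactly 6 is stopped without a required assessment

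*Combined protocol and SAP*

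**What the plan says.** Three sections of the combined protocol and SAP act on the Altman Self-Rating Mania Scale (ASRM).

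- **Section 8.1 (discontinuation of study intervention)** gives as a reason to stop stimulation: "A participant has an ASRM score greater than or equal to 6". It attaches no assessment to that score.
- **Section 9.2.2 (development of mania)** sets the trigger for clinical action: "If a participant develops any sign of mania (ASRM > 6"), in which case a named study clinician "will conduct an acute assessment to determine if the participant is experiencing mania".
- **Section 10.4.4 (safety analyses)** says: "A ASRM score of greater than 6 indicates the possible development of a manic episode". It sends participants above 6 for assessment and reports verified manic episodes as counts and percentages.

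Other provisions bear on the same participant but set no ASRM value. Section 8.1 says that after a clinically significant finding "the investigator or qualified designee will determine if any change in participant management is needed". Section 11.1.6 has the principal investigator review changes in mania ratings promptly and decide on continuation. Sections 9.2.3 and 10.4.4 provide a structured adverse event interview at D5, reviewed by a clinician.

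**The concern.** Two cut-offs govern one safety signal. At a score of 6 the protocol treats the signal as strong enough to end stimulation, yet the rule that requires someone to establish whether the participant is manic does not apply until 7.

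Two things are at stake. The first is clinical: a participant taken off treatment for a possible mania signal has no assessment that the protocol requires. The second is reporting: 10.4.4 counts verified episodes, and an episode can be verified only in someone who is assessed. A person stopped at 6 enters that count only if another route happens to lead to an assessment.

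**Working it through.** No power, sample size or alpha figure is involved, and the plan states no figure to reproduce. The check sets the rules side by side at neighbouring integer scores and then bounds the exposure.

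**Step 1. Is this a PDF reading error?** A lost underline could turn ≥ into > in 9.2.2, where a symbol is used. It cannot explain the mismatch, because 8.1 and 10.4.4 both spell out their comparison in words, and the words differ.

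**Step 2. The rules applied to a score in the stimulation week.**

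| ASRM score | Stop under 8.1 (≥ 6) | Assessment mandated under 9.2.2 and 10.4.4 (> 6) |
|---|---|---|
| 5 | no | no |
| 6 | yes | no |
| 7 or more | yes | yes |

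The rules part at one integer value, 6.

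**Step 3. Where the gap can arise.** In the schedule of activities (section 2.1, as extracted) the ASRM is marked at D0, D1, D5 and FU1 to FU7: 1 + 1 + 1 + 7 = 10 time points. Two of these, D1 and D5, fall in the stimulation week, where the 8.1 stop can act. None is marked at D2 to D4. Section 8.2 caps consent at 35, so at most 35 × 2 = 70 scores are exposed. This is a ceiling on scores and not an estimate of events, since the documents give no frequency for a score of 6.

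**Step 4. What a stop changes.** The schedule does not say whether the D1 score is taken before or after the first session.
- Stop at D1: 5 sessions averted if scored before, 5 − 1 = 4 if after.
- Stop at D5: at most the D5 session plus the one make-up session that section 6.5 allows, 1 + 1 = 2.

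**Step 5. With one cut-off.** At ≥ 6 in all three sections, a score of 6 leads to both stop and assessment. At > 6 in all three, it leads to neither. Either removes the mismatch; the first keeps the more cautious stop.

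**The case against.** The strongest reply is that the gap is narrow and the error is on the safe side. Nobody who scores 6 continues stimulation. The principal investigator's review in 11.1.6 has no cut-off and so covers a rise to 6. The 8.1 clause on clinically significant findings may apply, and on D5 every participant has an adverse event interview that a clinician reviews. Change in ASRM at D5, FU1 and FU2 is a secondary endpoint, so the scores are analysed whatever the episode count shows. D1 is labelled baseline, so a D1 score may well precede treatment, which would leave D5 as the on-treatment occasion. All of this stands and limits the size of the point. None of it mandates a mania assessment at 6.

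The reply also disposes of some stronger readings that a reader might infer:

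- *The sections conflict so that staff cannot comply with all of them.* They can. Sections 9.2.2 and 10.4.4 are silent at 6 and do not prohibit an assessment; stopping and assessing a 6 breaches nothing.
- *Section 10.4.4 declares that a 6 does not indicate possible mania.* It says what a score above 6 indicates and makes no statement about 6.
- *The ASRM stop is faulty because the suicidality stop in the same list rests on an assessment* ("A participant develops significantly increased suicidal risk, as determined by an acute assessment by"). Stopping on a score without waiting for an assessment is a defensible cautious rule. The contrast shows no error.
- *Section 9.2.2 contradicts 8.1 on study follow-up.* Section 9.2.2 says "If this occurs during the week of stimulation, participation in the study will be stopped", while 8.1 says "Discontinuation from the week of stimulation does not mean discontinuation from the study". The natural reading of the former is confirmed mania. The two then fit: the score stops stimulation, and confirmed mania ends participation.

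**Conclusion.** The inconsistency is real and minor. At an ASRM score of exactly 6 on D1 or D5, stimulation is stopped on a mania signal and no mania assessment is mandated. Entry to the 10.4.4 count of verified episodes then depends on discretionary review. The size is one integer value at two scheduled occasions, with at most 70 scores exposed and an unknown number equal to 6.

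It would overstate the case to say that such a participant goes unassessed: the protocol leaves the assessment optional. Nor is any efficacy result affected, because the mismatch concerns who must be assessed and leaves the stop itself and the HDRS-17 analysis unchanged.

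The conclusion rests on the schedule as extracted and on integer ASRM scores. The documents do not show which cut-off was intended.

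**What to change.** Use one cut-off in all three sections. Change the trigger in 9.2.2 and both statements in 10.4.4 to ASRM ≥ 6, and leave 8.1 as it is. This is the more cautious of the protocol's own two values, and it makes assessment mandatory for everyone stopped under the 8.1 score rule. The study physicians should confirm the intended value before the change is made.

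The cost is a few words, plus possibly a few more acute assessments for participants scoring exactly 6. Because the assessment rule in 9.2.2 is not limited to the stimulation week, these could arise at any of the 10 ASRM time points.

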8.2 PARTICIPANT DISCONTINUATION/WITHDRAWAL FROM THE STUDY

Participants are free to withdraw from participation in the study at any time and without having to give a reason. If the participant is willing to give a reason for discontinuation or withdrawal from the study, it will be recorded with the participant files. Participants who sign the informed consent form and do not receive stimulation will be replaced. Participants who sign the informed consent form and receive only part of the study intervention OR withdraw or are withdrawn or discontinue from the study prior to the 2-week follow-up will not be replaced. The maximum number of participants consented will be 35.

8.3 LOST TO FOLLOW-UP

A participant will be considered lost to follow-up if they fail to return for the scheduled follow-up visit and are unable to be contacted by the study site staff. All efforts will be made to ensure participants are not lost to follow-up, including developing rapport and ensuring enrolled participants are reminded of their session dates. To ensure that participants attend the follow-up session, research personnel will be flexible in timing, including offering sessions later in the day as well as some weekends.

Every effort will be made to contact participants who are lost to follow-up, including contacting via email and phone. However, if a participant is lost to follow-up, the missed sessions will be labeled as missing data and our pre-determined analysis plan takes into consideration missing data.

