4. OBJECTIVES AND OUTCOME MEASURES

OBJECTIVES	ENDPOINTS	JUSTIFICATION FOR ENDPOINTS
Primary		
To determine the effect of CLtACS on depression symptom severity	Change in HDRS-17 between two-week follow-up (FU2) and Day 1 (D1)	The HDRS-17 is the standard clinician-administered instrument to measure change in symptom severity in people with MDD
Secondary		
To determine the effect of CLtACS on depression symptom severity	Change in HDRS-17 between D5 and Baseline/ D1	The HDRS-17 is the standard clinician-administered instrument to measure change in symptom severity in people with MDD.
To determine the remission and response rate of CLtACS Response is defined as >= 50% reduction rate in HDRS-17 score relative to D1 Remission is defined as	Number of response/remission rates at D5 and FU2	Remission and response rates provide additional insights into the efficacy of a treatment.

OBJECTIVES	ENDPOINTS	JUSTIFICATION FOR ENDPOINTS
To determine time-course of symptom change	Change in Quick Inventory of Depressive Symptomatology (QIDS) at D5, FU1, FU2	Battery of self-report measures of mood and related constructs at the 7-day follow up (digitally
	Change in Altman Self-Rating Mania Scale (ASRM) at D5, FU1, FU2	delivered) provide additional insights into the symptom changes in between the
	Change in Snaith-Hamilton Pleasure Scale (SHAPS) at D5, FU1, FU2	clinician administered assessment on Day 5 and at FU2.
	Change in Depression Anxiety and Stress Scale (DASS-42) at D5, FU1, FU2	
	Change in State-Train Anxiety Inventory (STAI) at D5, FU1, FU2	
	Change in Quality of Life Enjoyment and Satisfaction Questionnaire, short form (Q-LES-Q-SE) at D5_EU1_EU2	
	Change in Clinical Global Impression Scale (CGI) at D5, FU2	
Exploratory		
Feasibility	Fraction of participants who complete the 5-day course of stimulation	Since the primary outcome is determined from the subgroup of people who have completed stimulation, examining the fraction of people who complete the stimulation paradigm is important to minimize bias in case of people discontinuing study participation due to lack of perceived efficacy or symptoms worsening.
To determine the effect of CLtACS on endogenous EEG alpha oscillations	Change in HD-EEG alpha oscillation power at D1 pre-stimulation, D1 post-stimulation, and FU2	The inclusion of EEG endpoints provides insights into the network-level mechanisms underlying the treatment effects.

OBJECTIVES	ENDPOINTS	JUSTIFICATION FOR ENDPOINTS				

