10.2 SAMPLE SIZE DETERMINATION

A recently concluded pilot clinical trial compared the effects of 10 Hz tACS (therapeutic frequency) against 40 Hz tACS (control frequency). A total of 32 participants enrolled, 30 completed the 5-day intervention, and 26 completed both a 2 and a 4-week follow-up session. With approximately 9 participants in each group, a significant reduction was found in alpha oscillation power on the fifth day of stimulation (p < 0.05) [6], which is the presumed mechanism of action of closed-loop tACS. Therefore, with a total of 35 participants we anticipate we will find a significant difference. Further support for this sample size from this previous study derives from a Cohen's dz = 1.58 for change in HDRS-17 score from baseline to the 2-week follow up. For an alpha = 0.05 (two-sided) and a power of 0.95, the required sample size is N=8 based on calculation by G*power 3.1.9.7. The plot below shows how power changes as a function of effect size for a sample size of N=10. As can be seen, the current design is well-powered for the expected effect size for clinical outcomes, and adequately powered (i.e. 80%) for effects as low as dz = 1 for any given outcome measure.

However, the expected effects of stimulation for secondary outcome measures at FU2 are currently unclear, and self-report measures tend to have more variability and thus reduced effect sizes when compared to clinician-administered measures like the HDRS-17. Moreover, studies looking to replicate prior findings are known to require larger sample sizes compared to the original study. To that end we conducted design sensitivity analyses. We reason that a target of N = 28 for a complete dataset allows for a sound evaluation of any given effect down to dz = 0.55 which is traditionally considered in psychological research to be a medium-sized effect for two-tailed α = 0.05 at 80% power.

In the previous trial, 80% of the participants completed all study sessions. We are thus anticipating consenting around 35 people to reach the goal of 28 people for analysis. The power calculation above demonstrates what statistical conclusions will be feasible with a sample size of 28 completers.

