10.4 STATISTICAL ANALYSES

10.4.1 GENERAL APPROACH

All testing described below assumes a significance threshold of alpha = 0.05. Continuous data will be described using means and standard deviations, while categorical data will be described using counts/percentages.

There will be no pre-specified covariates described in this protocol. Data will be assessed for normality and, if deemed necessary, corrective procedures will be applied (e.g., log normalization).

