10.4.2 ANALYSIS OF THE PRIMARY EFFICACY ENDPOINT (DEPRESSION SEVERITY)

We will perform a paired t-test to establish the statistical significance of the change in depression symptom severity (two-sided, alpha = 0.05). Additional, strictly exploratory analyses will take into account baseline scores as covariates (e.g., degree of treatment resistance measured by the Maudsley scale).

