10.4.3 ANALYSIS OF THE SECONDARY ENDPOINT (RESPONSE AND REMISSION RATE, FEASIBILITY)

We will compute the response and remission rates for the sample. There is no statistical testing applicable for this outcome since there are no groups to compare.

We will compute the fraction of participants who complete stimulation by dividing the number of people who received 5-days of stimulation by the total number of participants who received any amount of stimulation.

As applicable, 95% confidence intervals will be computed to describe precision of the estimate.

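### Section 8.3 says the analysis plan allows for missing data, but section 10 contains no missing-data method and no denominator for response and remission

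*Combined protocol and SAP*

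**What the plan says.** Section 8.3 labels sessions missed through loss to follow-up as missing data and adds that "our pre-determined analysis plan takes into consideration missing data". It gives no method and no cross-reference.

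The primary endpoint in section 4 is the HDRS-17 change from D1 to FU2. For its analysis, section 10.4.2 says: "We will perform a paired t-test to establish the statistical significance of the change in depression symptom severity". Section 10.4.1 provides for normality checks and transformation and says nothing about missing values. Section 10.4.3 says: "We will compute the response and remission rates for the sample". It does not say who forms the sample.

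Section 10.2 plans for attrition: "In the previous trial, 80% of the participants completed all study sessions", so about 35 are consented to reach 28 for analysis. Section 4, justifying the feasibility endpoint, says that "the primary outcome is determined from the subgroup of people who have completed stimulation" and names as a source of bias that people may leave because they feel no benefit or get worse.

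**The concern.** Section 8.3 hands the problem of missed visits to an analysis plan that does not take it up. Sections 10.1 to 10.4.7 contain no imputation, no repeated-measures model, no stated assumption about missingness, no sensitivity analysis and no non-responder rule. A paired t-test drops anyone without FU2 by construction.

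This is not only a matter of people who stop stimulation early. Someone who finishes all five sessions and then misses FU2 also drops out. The feasibility fraction in section 10.4.3 counts receipt of five days of stimulation, so it cannot show that loss.

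There is no comparator arm with similar dropout to offset the bias. The pilot is justified by the absence of effect-size data (section 5.2), and its time-course results are meant to inform larger studies (section 4). The size of the change and the response rate are therefore the results that others will use.

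**Working it through.** **1. The plan's own figures.** Inputs from section 10.2: 28 completers, dz = 0.55, two-sided alpha 0.05, 80% completion. Paired t-test power from the noncentral t distribution (27 df, noncentrality 0.55 × √28) is 80.1%. Number consented: 28 / 0.80 = 35. Both reproduce. The allowance covers lost precision, not selective loss.

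**2. How much FU2 loss to assume.** No document gives it. The nearest figures, all from section 10.2, are:
- 1 − 0.80 = 20% who did not complete all sessions
- 26 of 32 in the earlier trial attended both the 2-week and the 4-week visit, so 6/32 = 19% did not
- 30 of 32 finished stimulation; if the 26 are among these 30, 4/30 = 13% of finishers missed at least one of the two visits

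Some of those people may have attended week 2. I take 13% to 20% as an assumed range; true FU2 loss could be lower.

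**3. Bias in the complete-pairs mean.** Let X be improvement at D5 and Y improvement at FU2, both in SD units, with Y = rX + √(1 − r²)·e. Let logit P(FU2 missing) = a − bZ, where Z is X or Y and a is set to give the chosen loss. Assumed, not in the documents: r = 0.5 to 0.7 and b = 0.7 to 1.5 per SD. Regression of Y on X among the observed, averaged over everyone, stands in for a mixed model that uses D5. Simulation with 2 million draws per setting gives:

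| FU2 missing | Missingness depends on | Overstatement, complete pairs (SD) | Left after using D5 (SD) |
|---|---|---|---|
| 13% | D5 change | 0.04–0.11 | near 0 |
| 20% | D5 change | 0.07–0.16 | near 0 |
| 13% | FU2 change | 0.09–0.16 | 0.05–0.12 |
| 20% | FU2 change | 0.13–0.23 | 0.07–0.18 |

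In the last two rows 53% to 79% of the bias remains.

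**4. Effect on the primary test.** Give the missing exactly zero change and let m be the fraction observed. Then mean = m × 1.58 and SD = √(m(1 + 1.58²) − mean²).
- m = 0.80: mean 1.264, SD 1.095, dz = 1.15
- m = 0.87: mean 1.375, SD 1.073, dz = 1.28

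If the missing 20% have mean zero but the same spread as the others, SD = √(1 + 0.8 × 0.2 × 1.58²) = 1.183 and dz = 1.07. At dz = 1.15, power exceeds 99.9% with 28 or 35 people. At the plan's limit of dz = 0.55, zero change for 20% gives mean 0.44 and dz = 0.48, with 78% power at n = 35.

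**5. Response rate, illustration only.** Fourteen responders, a hypothetical count, is 14/28 = 50% or 14/35 = 40%. Section 10.4.3 does not say which would be reported.

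**The case against.** The plan does not ignore attrition. Section 8.1 invites people who stop stimulation to FU2, section 6.5 tracks attendance at each session, section 8.3 describes retention efforts, section 10.2 allows for 20% loss, and section 4 reports the completion fraction expressly because dropout could bias the result. The sentence in 8.3 could loosely mean that allowance. For an open-label pilot, an openly declared complete-case analysis with a sensitivity analysis would also remove the inconsistency.

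These provisions reduce or describe loss; none says how a missing FU2 enters the analysis. Section 10.3 relies on replacing people who do not complete the intervention, but section 8.2 says that those partly treated or leaving before FU2 are not replaced. Replacement would not reach people who finish stimulation and then miss FU2 in any case.

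The objection does stand against four stronger readings that a reader might infer:
- That the plan expects 7 of 35 to lack FU2. The 80% refers to all sessions, and the 26 to two visits together.
- That using D5 cures the bias. It does so only if missingness depends on D5; if it depends on how people fare afterwards, most of the bias can remain.
- That the primary result would lose significance. Near dz = 1.58 it would not.
- That the response rate will fall from 50% to 40%. The counts are invented, and 35 is the maximum consented, not the number stimulated.

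**Conclusion.** The inconsistency is established from the text alone: section 8.3 refers to a method that section 10 lacks. Followed as written, the plan yields a complete-pairs change and a response rate with no defined denominator, both open to a bias that section 4 itself recognises.

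The size is modest and conditional. At 13% to 20% FU2 loss the mean improvement is overstated by about 0.04 to 0.16 SD if missingness follows D5 change, and by about 0.09 to 0.23 SD if it follows the FU2 result. The loss range, correlations, slopes and direction of selection are all assumptions. The conclusion about significance is safe for an effect near dz = 1.58 and less so near 0.55. The change should be made, and best before data are seen.

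**What to change.** - **Section 10.4.2.** Estimate the D1-to-FU2 change from a mixed model for repeated measures on HDRS-17 at D1, D5 and FU2, with visit as a fixed factor, unstructured covariance, and missing at random stated as the assumption. Include everyone who received any stimulation and has D1 and at least one later HDRS-17. Keep the paired t-test as supportive.
- **Sensitivity analysis.** Assume worse outcomes in the missing, for example zero change on average. Handle the variance properly, because filling in exact zeros understates it. Include people who have only D1, whom the mixed model leaves out.
- **Section 10.4.3.** Use everyone who received any stimulation as the denominator at D5 and FU2, count missing as not responded or not remitted, and report the observed-case rate beside it.
- **Consistency.** Reconcile this population with the statement in section 4 that the primary outcome comes from stimulation completers, and make section 8.3 refer to these rules.

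No new data are needed, since HDRS-17 is already collected at D5. The cost is a protocol amendment with IRB approval (section 1), a little analysis work, and a response rate that may be noticeably lower than one based on attenders.
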